### **10.3 Planned Analyses**

#### **10.3.1 Primary Objective**

The primary objective will be to determine the progression-free survival (PFS) rate after 2 and 3 years. This will be done in two ways. First, the proportion of patients alive and progression-free at 2 and 3 years will be calculated, along with an exact 90% confidence interval, both two-sided as well as a lower 90% confidence limit. The number of patients alive and progression-free at 2 and 3 years will be used to address the primary hypothesis as indicated in section 10.2 above. In addition, a Kaplan-Meier curve will be calculated to obtain the actuarial estimate of two-year progression-free survival.

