Diagnosis and Main Inclusion Criteria	
 
1. Histologically confirmed MCL.
 
2. Disease response (either CR or PR), without known progression, to one (1) prior systemic chemotherapy regimen, with or without consolidative auto SCT. The options are:           
 
a. R-CHOP (with or without cytarabine-containing cycles, including "Nordic" [1] and MCL-NET protocols [2]) with or without auto SCT
 
b. R-Hyper-CVAD with or without auto SCT
 
c. R-Bendamustine with or without auto SCT
 
 
 
3. Prior radiotherapy is permissible.
 
4. Age <math>\geq</math> 18 years.
 
5. ECOG performance status <math>\leq</math> 2.
 

Treatment Plan	Ibrutinib will be given at a fixed dose of 560 mg PO daily throughout the study, to patients who have completed at least 4 cycles of intensive induction chemotherapy (with or without ASCT). The dose is based upon safety and efficacy data. For the purposes of this study, one cycle will be defined as 28 days. This will be continued up to 4 years in the absence of progression of disease, intolerable toxicity, or patient preference (including withdrawal of consent).

Study Numbers: NU 14H06  
PCI-32765MCL2003Initial version: September 24, 2014  
AMD 11: ver. date 08.06.2022

Statistical Methodology	
The primary endpoint is three-year PFS. Our null hypothesis is that ibrutinib maintenance will yield no improvement upon the 60% three-year PFS observed in studies described above. We consider an observed three-year PFS of 80% both feasible and of significant clinical improvement. The study will have 10% Type I error and 90% power to detect an effective treatment using a one-stage design based on the true proportion of patients achieving 3-year PFS is at least 80% versus the null hypothesis that the true complete response rate is at most 60%. Based upon these parameters, our sample size will be 36 evaluable patients. For the final analysis, if 25 or fewer patients are alive and without progression from among all 36 evaluable patients accrued, we will consider this regimen ineffective for this patient population. If, on the other hand, 26 or more patients are alive and without progression, this will be considered sufficient evidence that this treatment may be recommended for further testing in subsequent studies, particularly in a randomized setting.

--------------------------------	--

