## 2.0 STUDY OBJECTIVES & ENDPOINTS

### 2.1 Primary Objective & Endpoint

The primary objective will be to determine the progression-free survival (PFS) rate after 3 years.

Progression-free survival (PFS) will be defined as the absence of disease progression or death from any cause. The rate of PFS will be calculated after 3 years.

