## 6.0 ENDPOINT ASSESSMENT

### 6.1 Primary Endpoint

The primary endpoint will be progression-free survival (PFS) at 3 years. PFS will be measured from start of treatment to time of progression or death from any cause. Progression-free survival will be defined as the absence of either progression or death from any cause. Progression will be evaluated using Cheson 2007 criteria (Revised Response Criteria for Malignant Lymphoma, modified – please see Appendix II). Evidence of clinical progression will be documented by imaging (CT scan or MRI) for patients who have measurable disease. Any patient who receives at least one dose of study treatment will be evaluable for this endpoint.

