## **10.2 Sample Size and Power Calculations**

The primary endpoint is three-year PFS. Our null hypothesis is that ibrutinib maintenance will yield no improvement upon the 60% three-year PFS observed in

studies described above. We consider an observed three-year PFS of 80% both feasible and of significant clinical improvement. The study will have 10% Type I error and 90% power to detect an effective treatment using a one-stage design based on the true proportion of patients achieving 3-year PFS is at least 80% versus the null hypothesis that the true complete response rate is at most 60%.

Based upon these parameters, our sample size will be 36 evaluable patients. For the final analysis, if 25 or fewer patients are alive and without progression from among all 36 evaluable patients accrued, we will consider this regimen ineffective for this patient population. If, on the other hand, 26 or more patients are alive and without progression, this will be considered sufficient evidence that this treatment may be recommended for further testing in subsequent studies, particularly in a randomized setting.

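### Section 10.3.1 applies both the 2-year and the 3-year count to a 26-of-36 rule built for 3-year PFS only, and names its Kaplan-Meier estimate at two years

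*Combined protocol and SAP*

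**What the plan says.** The endpoint sections agree on a single time point. Section 2.1 states "The rate of PFS will be calculated after 3 years", and section 6.1 states "The primary endpoint will be progression-free survival (PFS) at 3 years". Section 10.1.1 and the objectives in the Study Summary say the same.

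Section 10.2 builds a one-stage design on that endpoint: "Our null hypothesis is that ibrutinib maintenance will yield no improvement upon the 60% three-year PFS observed in" earlier studies, against an alternative of 80%, with 10% type I error, 90% power and 36 evaluable patients. Its success criterion reads "26 or more patients are alive and without progression, this will be considered sufficient evidence". Neither that sentence nor its counterpart for 25 or fewer gives a time point.

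Section 10.3.1 departs from this three times:

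- The objective becomes "The primary objective will be to determine the progression-free survival (PFS) rate after 2 and 3 years".
- Both counts go to the test: "The number of patients alive and progression-free at 2 and 3 years will be used to address the primary hypothesis", with a pointer back to section 10.2.
- The actuarial analysis is named at two years only: "a Kaplan-Meier curve will be calculated to obtain the actuarial estimate of two-year progression-free survival".

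Section 10.3.1 does plan the 3-year proportion with exact 90% limits. What it lacks is a named 3-year Kaplan-Meier estimate.

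A related slip appears in section 10.2 and in the Statistical Methodology row of the Study Summary, where the null is worded as "the null hypothesis that the true complete response rate is at most 60" per cent. The quantity under test is 3-year PFS, not a response rate.

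**The concern.** The 26-of-36 cut-off has its stated error rate only for a count whose null probability is 60%, and the documents attach 60% to three years. Two-year PFS cannot be lower than three-year PFS, so testing the 2-year count against the same cut-off tests an easier target.

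Anyone following section 10.3.1 literally has two counts and one undated cut-off. There are three ways to proceed: treat the 2-year count as descriptive, require both counts to pass, or let the 2-year count decide. The text does not choose among them. The 2-year count is available a year earlier and is never the smaller of the two, so the ambiguity can only favour a declaration of success. A choice made after the data are seen would look data-driven.

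The Kaplan-Meier point stands apart from this. Under section 4.8, withdrawal of consent ends follow-up, so some patients may have unknown status at 3 years. The actuarial estimate is the planned analysis that handles such censoring, yet it is to be read a year before the endpoint under test.

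**Working it through.** **Inputs.** From section 10.2: n = 36, success if X ≥ 26, null 60% and alternative 80%, both at 3 years. The documents give no 2-year PFS under the null, so it is assumed below over a range.

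**Step 1. Reproduce the plan's design.** With X ~ Binomial(36, p):

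- Type I error = P(X ≥ 26 | p = 0.60) = 0.0904.
- Power = P(X ≥ 26 | p = 0.80) = 0.9111.
- Neighbouring cut-offs do not meet the specification: 25 gives a type I error of 0.162, and 27 gives power of 0.832.
- Among sample sizes from 20 to 44, 36 is the smallest with exact error at most 10% and power at least 90%.

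The stated design is therefore correct for the 3-year count.

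**Step 2. Both counts must reach 26.** Let N2 and N3 be the numbers alive and progression-free at 2 and 3 years. Everyone counted in N3 is also in N2, so N3 ≤ N2. Hence P(N2 ≥ 26 and N3 ≥ 26) = P(N3 ≥ 26) = 0.0904, and the error is unchanged.

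**Step 3. The 2-year count alone can declare success.** A rule allowing success on either count is the same rule, again because N3 ≤ N2. The error is P(X ≥ 26 | p = S2), where S2 is 2-year PFS when 3-year PFS is 60%. It equals 0.10 at S2 = 0.6047, so any null curve with 2-year PFS above about 60.5% breaks the stated limit.

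For illustration, take a Weibull curve through 60% at 3 years, so that S2 = 0.60^((2/3)^k). Shape k = 1 is constant hazard.

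| Shape k | S2 | Type I error, 2-year count alone |
|---|---|---|
| 0.5 | 0.6590 | 0.2702 |
| 0.75 | 0.6860 | 0.3946 |
| 1 | 0.7114 | 0.5265 |
| 1.5 | 0.7573 | 0.7587 |
| 2 | 0.7969 | 0.9029 |

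These shapes do not bound the answer: k = 0.25 gives 0.1662 and k = 3 gives 0.9915.

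**Step 4. Opposite verdicts.** Because N3 ≤ N2, the probability under the null that the 2-year count passes and the 3-year count fails is P(N2 ≥ 26) − P(N3 ≥ 26). With constant hazard this is 0.5265 − 0.0904 = 0.4361. For shapes 0.5 and 2 it is 0.1798 and 0.8126 (differences taken before rounding).

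**The case against.** The strongest reply is that 3 years is plainly meant. Section 10.3.1 does not state the 26-of-36 rule itself; it defers to section 10.2. That section opens by naming three-year PFS as the primary endpoint, specifies a one-stage design, and derives the cut-off from the 60% and 80% three-year rates. The exact calculation confirms that link. With no 2-year hypothesis anywhere, a decision on the 2-year count would have to override the section that 10.3.1 relies on. The change history in Appendix IV points the same way: Amendment 1 lists 10.3.1 among the sections moved from 2 to 3 years to correct a clerical error, so leftover wording is the likeliest explanation. The inflated error rates also rest on assumed curve shapes.

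Most of this stands. Three years is the better-supported reading, and the figures in steps 3 and 4 apply only if the 2-year count may decide alone. It does not remove the defect. The current analysis section still says that both counts address the primary hypothesis, and a prespecified primary test should not depend on the analyst inferring that its own text is mistaken.

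It is also fair to say that the Kaplan-Meier estimate is supplementary and that one curve can be read at any time. The named read-off is nevertheless at the wrong time point under every reading of the count rule.

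**Conclusion.** The concern holds. Section 10.3.1 contradicts sections 2.1, 6.1, 10.1.1 and 10.2 on the time point of the primary analysis, gives no rule for using two counts, and names the actuarial estimate at a time other than that of the endpoint. These are matters of text and need no assumption.

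The effect on type I error is conditional. It is nil if the 2-year count is descriptive or if both counts must pass. If the 2-year count could decide alone, the 10% limit would be kept only by a null PFS curve almost flat between years 2 and 3. How far the limit would be exceeded depends on that curve, which the documents do not describe. Because the ambiguity concerns the trial's success criterion, it should be removed before the primary analysis.

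**What to change.** 1. In section 10.3.1, restate the primary objective as PFS at 3 years, and say that only the number alive and progression-free at 3 years is compared with the 26-of-36 cut-off.
2. In section 10.2 and the Study Summary, add the 3-year time point to both decision sentences (25 or fewer, 26 or more).
3. In section 10.3.1, name the Kaplan-Meier estimate at three years, with 90% confidence limits.
4. Keep the 2-year proportion and 2-year Kaplan-Meier estimate if wanted, labelled as descriptive and with no part in the decision.
5. In section 10.2 and the Study Summary, state the null as a true 3-year PFS of at most 60% in place of the complete response rate.

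The cost is a wording amendment to these three places. Sample size, cut-off, procedures and patient care are unchanged.

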#### **10.3.2 Secondary Objectives**

To assess toxicity, all adverse events will be summarized as to type, severity, frequency, timing and attribution. Descriptive frequencies and proportions will be used for this analysis.

To determine rates of conversion from PR to CR, only patients who had a PR at the time of registration and who complete  $\geq 1$  complete cycle of ibrutinib maintenance therapy will be evaluable for this endpoint. These rates will be calculated as a proportion together with exact 90% confidence limits.

To determine median overall survival (OS) after 4 years, Kaplan-Meier curves will be determined for overall survival and the five-year point on this curve, along with 90% confidence limits, will be determined. Patients will be evaluated monthly for the first 6 months on treatment, then every 3 months thereafter. Patients who go off treatment will continue to be followed for survival up to a maximum of 4 years post-first dose. Follow-up will occur every 3 months (up to 2 years after the first dose of treatment) and then every 6 months thereafter (up to 4 years post-first dose).

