## 4.0 TREATMENT PLAN

### 4.1 Overview

Induction therapy will not be part of the protocol-specified treatment. Patients must have received four (4) or more cycles of R-CHOP (with or without alternating R-DHAP), R-Hyper-CVAD, or bendamustine + rituximab (all with or without auto SCT), with documented PR or CR by Cheson 2007 criteria. Within 14 days of study registration, patients will begin treatment with ibrutinib at a fixed dose of 560 mg PO daily. One cycle will be defined as 28 days. Patients may continue to receive cycles of ibrutinib therapy up to 4 years in the absence of progression of disease or intolerable toxicity, or patient preference (including withdrawal of consent).

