#### **4.3 Toxicity Management & Dosing Holds/Dose Modifications**

##### **4.3.1 Dose Holds**

At each study visit (see section 5.0 for schedule), the subject will be evaluated for possible drug toxicities. All previously established or new toxicities observed at any time are to be recorded in the appropriate electronic case report form (eCRF) and managed as described below. The lead principal investigator and QAM should be contacted regarding any unmanageable toxicity.

Study drug may be held for a maximum of 28 consecutive days. Once the ibrutinib dose is reduced, it cannot be re-escalated. When a dose is missed or held, it will not be made up, regardless of duration.

Observations and scheduled assessments will continue regardless of amount of drug the patient has had and should always be based on time from C1D1. (For example, if a patient is held on C2D14 for a week, the day they re-start will be C2D21, and the patient will still have scheduled assessments as planned on C3D1) Please contact QA if you have any questions on timing of holds or study assessments.

*See section 4.4.3 for subjects requiring the initiation of anticoagulants while receiving study drug and for instructions on dose modifications or temporary hold during concomitant administration of CYP3A4/5 inhibitors or inducers. For guidance on dose hold during the perioperative period for subjects who require surgical intervention or an invasive procedure while receiving study drug please see section 4.4.4.*

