## 5.0 STUDY PROCEDURES

Table: Schedule of Events

Test/Assessment	Pre-Study	Screening	On-Treatment 		Off-Treatment	
		Baseline Tests 	Cycles 1-6 	Cycles 7+ 	EOT 	Follow-Up 
Documentation of induction chemotherapy 	X					
Informed consent		X				
Medical history		X				
Concomitant medications		X	X	X		
Physical exam 		X	X	X	X	
ECOG status		X	X	X		
Hematology 		X	X	X	X	
Chemistries 		X	X	X	X	
Pregnancy test 	X					
Hep B & C serologies 		X				
Tissue for research 		X				
Research blood samples 			X	X		
CT scan (C/A/P) or MRI 		X	X	X 		
Peripheral blood for flow cytometry 			X	X		
Bone marrow biopsy 		X		X		X 
EGD/Colonoscopy 		X		X		X 
Drug administration & accountability 			X			
Adverse events 		X	X	X	X	X
Survival					X	X

Must include at least 4 cycles of R-CHOP (with or without alternating R-DHAP), R-Hyper-CVAD, or bendamustine + rituximab (all with or without auto SCT). Last dose of cytotoxic chemotherapy must be at least 14 days prior to registration (but no more than 120 days prior). Patients who underwent auto SCT must show engraftment and meet all required baseline hematological parameters.

While on treatment, one cycle will be defined as 28 days (+/- 2 days). Assessments will occur on day 1 of each cycle ( $\pm$  2 days, for the first 6 months), then every 3 cycles ( $\pm$  10 days, up to 4 years). If after 2 years a patient is clinically stable and lives far from the study site, he or she may elect to be seen every 6 cycles ( $\pm$  10 days), with a sufficient drug supply, as detailed in section 4.2. Labs should be resulted prior to treatment to assess the need for dose modifications (see section 4.3 for details). When a dose is missed or held, it will not be made up, regardless of duration. Observations and scheduled assessments will continue regardless of amount of drug the patient has had, and should always be based on time from C1D1. Please contact QA if you have any questions on timing of holds or study assessments.

CBC with platelets/differential

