Comprehensive chemistry panel, Mg, and LDH. Comprehensive chemistry panel includes glucose, calcium, albumin, ALT, AST, sodium, potassium, total bilirubin, alk phos, creatinine.

If applicable for WOCBP (urine or serum).

Baseline/screening tests required to be completed as follows: within 90 days prior to registration for imaging, bone marrow biopsy and EGD/Colonoscopy (if applicable) and within 14 days prior to registration for all other baseline assessments (except informed consent, which can be signed within 30 days prior to registration).

Imaging should be performed at baseline, after cycles 3 and 6, every 6 months/cycles for the first 2 years, once at 3 years, and as clinically indicated thereafter (including EOT, as clinically appropriate, for patients who complete 4 years of therapy, or patients that come off study treatment early for a reason other than progression). In general, it is *preferred* that imaging be CT-based; at a minimum, the same modality should be used consistently for each patient.

Ibrutinib will be administered at a dose of 560 mg PO daily throughout the course of treatment unless a dose reduction occurs (see section 4.3.2 for details).

Patients will be asked to keep a study calendar for the duration of treatment See section 4.2 for details on dispensing and visit frequency.

Patients will be evaluated on Day 1 of each cycle ( $\pm 2$  days) for the first 6 cycles (prior to the start of each cycle). NOTE: Cycle 1 Day 1 should begin within 14 days after registration, however Day 1 labs (hematology and chemistry tests) need only be repeated if screening labs were performed  $>7$  days prior to C1D1.

Patients will be evaluated every 3 cycles (on Day 1,  $\pm 10$  days) beginning with cycle 7. After 2 years on therapy, patients will continue to be seen *clinically* every 3 cycles, however collection of data for study purposes will only be required every 6 cycles (approximately every 6 months) for the remainder of study treatment.

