## 7.2 Definitions & Descriptions

### 7.2.1 Adverse event (AE)

An adverse event (AE) is any untoward medical occurrence in a patient receiving study treatment and which does not necessarily have a causal relationship with this treatment. An AE can therefore be any unfavorable and unintended sign (including an abnormal laboratory finding), symptom, or disease temporally associated with the use of an experimental intervention, whether or not related to the intervention.

Recording of AEs should be done in a concise manner using standard, acceptable medical terms. In general, AEs are not procedures or measurements, but should reflect the *reason* for the procedure or the diagnosis based on the abnormal measurement. Preexisting conditions

that worsen in severity or frequency during the study should also be recorded (a preexisting condition that does not worsen is not an AE). Further, a procedure or surgery is not an AE; rather, the event *leading to* the procedure or surgery is considered an AE.

If a specific medical diagnosis has been made, that diagnosis or syndrome should be recorded as the AE whenever possible. However, a complete description of the signs, symptoms and investigations which led to the diagnosis should be provided. For example, if clinically significant elevations of liver function tests are known to be secondary to hepatitis, "hepatitis" and not "elevated liver function tests" should be recorded. If the cause is not known, the abnormal test or finding should be recorded as an AE, using appropriate medical terminology (e.g/ thrombocytopenia, peripheral edema, QT prolongation).

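### Scheduled labs thin from every 28 to every 84 days after cycle 6 (and study data to every 168 days after year 2), so the adverse-event summary by timing can show silent laboratory toxicity falling when its true rate is constant; one extra table would guard against this.

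*Combined protocol and SAP*

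**What the plan says.** The toxicity analysis is one short paragraph in section 10.3.2: "all adverse events will be summarized as to type, severity, frequency, timing and attribution", with descriptive counts and percentages. It does not define timing, name periods, give a denominator or mention how often patients are assessed.

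The schedule is in section 5.0, where the table lists hematology and chemistries at the on-treatment visits:
- Footnote 2, for the first six months: "Assessments will occur on day 1 of each cycle". It also says "Labs should be resulted prior to treatment to assess the need for dose modifications", which ties the labs to the visits. Section 4.1 sets the unit: "One cycle will be defined as 28 days".
- Footnote 10, from cycle 7: "Patients will be evaluated every 3 cycles (on Day 1".
- Footnote 10, after 2 years: clinical visits continue every 3 cycles, but "collection of data for study purposes will only be required every 6 cycles (approximately every 6 months) for the remainder of study treatment".

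Section 7.2.1 makes laboratory abnormalities reportable: "An AE can therefore be any unfavorable and unintended sign (including an abnormal laboratory finding), symptom, or disease". Section 4.3.1 adds that capture is not confined to visits: "All previously established or new toxicities observed at any time are to be recorded".

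**The concern.** A cytopenia or chemistry change that causes no symptoms enters the data only if a blood sample is taken while it lasts. Fewer samples mean fewer such events recorded, whatever the drug is doing. Because sampling becomes sparser as treatment goes on, the bias has a known direction: towards toxicity that appears early and then settles.

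Dividing by time on drug does not help, because the missing events are lost from the numerator. A display of onset days instead of period counts does not escape either, since only detected onsets can be plotted.

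Toxicity is the first-listed secondary objective, treatment runs up to 4 years, and section 1.2.3 describes Grade 3-4 events in pooled ibrutinib data as mostly hematologic. Late tolerability of maintenance is something readers will look for in this table.

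**Working it through.** The plan states no figure on this point, so there is none to reproduce.

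**Inputs from the documents.** Cycle = 28 days (4.1). Scheduled lab interval T = 28 days in cycles 1-6 and 3 × 28 = 84 days from cycle 7. Required study-data interval after 2 years = 6 × 28 = 168 days (5.0, footnotes 2, 9 and 10).

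**Assumptions, not in the documents.** Constant true onset rate (the ratios do not depend on its level); episode durations over a range; detection first at scheduled labs only, then partly between visits.

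**Step 1, count the samples.** The day 1 draw of cycle 1 is pre-dose and cannot show on-treatment toxicity. In the first 168 days on drug the scheduled draws are day 1 of cycles 2 to 7: 6. In the next 168 days they are day 1 of cycles 10 and 13: 2.

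**Step 2, probability that an episode meets a scheduled sample.** For fixed duration d: min(1, d/T). For exponential duration with mean D: (D/T)(1 − exp(−T/D)).

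| Duration | T = 28 | T = 84 | T = 168 | 84 vs 28 | 168 vs 28 |
|---|---|---|---|---|---|
| Fixed 14 d | 0.50 | 0.167 | 0.083 | 0.33 | 0.17 |
| Fixed 28 d | 1.00 | 0.333 | 0.167 | 0.33 | 0.17 |
| Fixed 42 d | 1.00 | 0.50 | 0.25 | 0.50 | 0.25 |
| Fixed 56 d | 1.00 | 0.667 | 0.333 | 0.67 | 0.33 |
| Fixed 84 d | 1.00 | 1.00 | 0.50 | 1.00 | 0.50 |
| Exponential, mean 14 d | 0.432 | 0.166 | 0.083 | 0.39 | 0.19 |
| Exponential, mean 28 d | 0.632 | 0.317 | 0.166 | 0.50 | 0.26 |
| Exponential, mean 56 d | 0.787 | 0.518 | 0.317 | 0.66 | 0.40 |
| Exponential, mean 168 d | 0.921 | 0.787 | 0.632 | 0.85 | 0.69 |

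With a constant onset rate, the last two columns are the ratios of recorded events per patient-time. The last column applies only if the 6-cycle visits alone supply data after year 2.

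**Step 3, check on the actual visit days.** Simulating 100,000 patients with one onset per patient-year on the protocol's visit days gives ratios for months 7-12 against months 1-6 of 0.38-0.39, 0.50, 0.66 and 0.85 for exponential means of 14, 28, 56 and 168 days. This agrees with the formula. With 6-cycle data after year 2 and mean 14 days, the recorded rate falls from 0.428 to 0.082 per patient-year: 0.082/0.428 = 0.19.

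**Step 4, allow detection between visits.** If a share u of episodes is also found off schedule, detection is u + (1 − u)p. For mean 14 days:
- u = 0.25: (0.25 + 0.75 × 0.166)/(0.25 + 0.75 × 0.432) = 0.375/0.574 = 0.65 (simulated 0.66).
- u = 0.50: 0.583/0.716 = 0.81 (simulated 0.82).
- u = 1: 1.00.

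**Step 5, test the remedy.** In the same simulation, the proportion of scheduled post-dose labs falling inside an episode, months 1-6 against months 7-12, is 3.7% and 3.8% for mean 14 days, about 6.8% and 7.7% for mean 28 days, and 11.6% and 15.2% for mean 56 days. The false fall is gone. The rise with longer episodes occurs because simulated patients start free of abnormality and prevalence builds up, so this measure is a prevalence and not an onset rate.

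**The case against.** The strongest reply is that section 10.3.2 promises no by-period table at all. It names timing as one descriptor, and the durations that drive the effect are assumptions. The protocol also records toxicities whenever they are observed (4.3.1) and all adverse events throughout the study (7.1). Nor is duration independent of detection: under section 4.3.2 a detected listed toxicity leads to a hold, while an undetected one continues on drug. Finally, the summary is descriptive, with no test or decision attached.

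Much of this stands. A reader might infer that the table will show a decline, or that detection drops threefold. The documents support neither as a general statement. The ratio of one third applies only to episodes of 28 days or less found solely at scheduled labs; it is 0.67 for fixed 56-day episodes and 1.0 at 84 days, and it moves towards 1 as off-schedule detection rises. A summary already expressed per assessment would show no false fall.

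What does not stand is that open wording removes the problem. Both period counts and onset days inherit the sampling change, and off-schedule capture removes the effect only if it is complete, which is least likely for silent abnormalities.

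A fair objection to the remedy is sparseness. At the pooled Grade 3-4 rates in section 1.2.3 (anemia 5.8%, thrombocytopenia 5.1%, neutropenia 4.5%), 36 patients would give about 36 × 0.058 = 2.1, 36 × 0.051 = 1.8 and 36 × 0.045 = 1.6 affected patients. That is a reason to keep the table coarse, not to leave it out.

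**Conclusion.** The point holds as a cheap improvement. Sampling falls from every 28 to every 84 days after cycle 6, required study data fall to every 168 days after year 2, and the planned timing summary allows for neither. Transient, symptomless laboratory toxicity can therefore appear to decline when its rate is constant.

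The size cannot be fixed from the documents. With scheduled detection only, the later-to-early ratio is about 0.33 for fixed episodes of 28 days or less, 0.39 to 0.66 for exponential durations of mean 14 to 56 days, and 1.0 for fixed episodes of 84 days or more. Off-schedule detection pulls it towards 1. After year 2 it could reach about 0.19 for mean 14-day episodes, but only if the 6-cycle visits alone supply data.

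The consequence is confined to a descriptive secondary summary. The primary rule (26 or more of 36 alive and progression-free) does not use laboratory data, and the boundaries in section 10.3.4 count drug-related SAEs.

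**What to change.** Add to section 10.3.2, for laboratory-defined adverse events:

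1. Timing periods that follow the sampling changes: post-dose labs through day 1 of cycle 7 (the last draw at a 28-day interval), then to 2 years, then after 2 years.
2. For each period, the proportion of scheduled post-dose lab assessments with a Grade 3-4 value, with the number of assessments and of patients assessed. Use every scheduled post-dose draw and exclude the pre-dose draw on day 1 of cycle 1. Restricting to visits common to all periods (cycles 1, 4, 7 and so on) would discard usable draws and leave day 1 of cycle 4 as the only on-drug visit within cycles 1-6.
3. The all-data incidence table alongside, with a footnote stating that scheduled sampling changes after cycle 6 and required data collection changes after year 2.

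No visit, sample or clinical rule changes. The cost is one descriptive table and a footnote from data already collected. Its limits should be stated: cells will be sparse, it measures prevalence at visits and not onset, and it is conditional on patients still on treatment, so patients who stop for toxicity leave the denominator and can produce a decline of their own.
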